## 4. INVESTIGATIONAL PLAN

### 4.1. Overall Study Design

This is a Phase 2 study of the combination of the PI3K $\delta$  inhibitor INCB050465 and the JAK 1/2 inhibitor ruxolitinib in subjects with PMF or secondary MF (PPV-MF or PET-MF) who have suboptimal response while receiving ruxolitinib monotherapy. Suboptimal response is based on assessment of suboptimal reductions in spleen size or symptoms and is defined in the inclusion criteria (Section 3.2). At least 6 months of prior ruxolitinib therapy is required, including ruxolitinib administration at a stable dose for at least 8 weeks before randomization. The study is composed of 4 parts:

**Part 1** was an open-label safety run-in portion designed to assess the safety and tolerability of the combination of INCB050465 with ruxolitinib and to select appropriate doses of INCB050465 for Part 2 in this patient population. Part 1 has been completed.

**Part 2** was planned to be a block-randomized open-label study with 2 treatment groups: TG10 and TG20. Both treatment groups use daily doses for the first 8 weeks, then weekly doses at the same strength through EOT. Enrollment in Part 2 was suspended with implementation of Amendment 5.

**Part 3** was planned to be an open-label study to compare daily versus weekly long-term doses. All subjects would begin with INCB050465 20 mg QD. After 8 weeks, subjects in TG5 would continue receiving INCB050465 at 5 mg QD, and subjects in TG20 would continue receiving INCB050465 at 20 mg once weekly. Enrollment in Part 3 will be suspended with implementation of Amendment 6.

**With Amendment 6, Part 4** is added to directly compare different daily dosing regimens and the impact of an initial higher dose of INCB050465 on long-term response. Subjects in Part 4 will be randomized to 1 of 2 groups: TG5D will begin on Day 1 with a daily dose of 5 mg, and subjects will continue receiving 5 mg QD indefinitely or until discontinuation criteria are met; TG5I/M will begin on Day 1 with a daily dose of 20 mg (the induction dose), and after 8 weeks subjects will switch to 5 mg QD (the maintenance dose). Treatment for subjects randomized to TG5I/M will continue indefinitely or until discontinuation criteria are met.

#### **Randomization:**

During Part 2, subjects were randomized 1:1 to the 2 treatment groups using block randomization, stratified by Eastern Cooperative Oncology Group (ECOG) performance status at screening (ECOG 0-1 vs ECOG 2).

During Part 3, subjects were randomized on a 3:2 ratio between TG5 and TG20. Stratification was by ECOG status as in Part 2.

During Part 4, subjects will be randomized on a 3:2 ratio between TG5D and TG5I/M until 25 total subjects have been randomized, with subsequent randomization on a 1:1 ratio until approximately 30 subjects have been enrolled in each group. Stratification will be by ECOG status as in Part 3.

#### 4.1.1. Part 1: Safety Run-In Portion

The safety run-in portion was to test up to 3 doses of INCB050465 in combination with ruxolitinib for a 28-day assessment (4 weeks). Initially, 3 subjects were enrolled in Cohort 1 to receive INCB050465 10 mg together with ruxolitinib, at the dose ongoing at the time of enrollment. After 28 days, subjects who took at least 22 of 28 daily doses of INCB050465 AND ruxolitinib OR had a DLT during the first 28 days (see [Table 3](#)) were included in the evaluation cohort. Additional subjects were to be enrolled into Cohort 1 if discontinuations resulted in fewer than 3 evaluable subjects. After evaluation, the actions listed in [Table 2](#) were to occur.

**Table 2: Safety Run-In Cohorts**

Cohort	No. of Subjects	Regimen	DLTs Observed	Action Taken
1	3	INCB050465 10 mg QD for 8 weeks followed by 10 mg once weekly plus ruxolitinib 5 mg BID to 25 mg BID a	0	Proceed to Cohort 2.
			1	Enroll 3 additional subjects, and evaluate the total of 6 subjects after 28 days. If < 2 subjects have a DLT, then proceed to Cohort 2. If $\geq 2$ subjects have a DLT, then proceed to Cohort 3.
			> 1	Proceed to Cohort 3.
2	3 + 3	INCB050465 20 mg QD for 8 weeks followed by 20 mg once weekly plus ruxolitinib 5 mg BID to 25 mg BID a	0 or 1	Enroll 3 additional subjects, and evaluate the total of 6 subjects after 28 days. If < 2 subjects have a DLT, then proceed to Part 2 using doses of 10 mg and 20 mg INCB050465.
			$\geq 2$	Proceed to Cohort 3.
3	6	INCB050465 5 mg QD for 8 weeks followed by 5 mg once weekly plus ruxolitinib 5 mg BID to 25 mg BID a	0 or 1	If < 2 subjects have a DLT and if Cohort 1 exceeded the DLT allowance, then proceed to Part 2 as a single-group study of 5 mg INCB050465. If Cohort 1 did not exceed DLT allowance, proceed to Part 2 with doses of 5 mg and 10 mg INCB050465.
			$\geq 2$	Terminate study. Alternatively, sponsor may elect to assess doses lower than 5 mg. If Cohort 1 did not exceed the DLT allowance, but Cohort 3 showed DLTs, additional cohort expansion might be conducted to assess these and other doses of INCB050465, pending sponsor review and discussion of available data.

a The dose of ruxolitinib will be that which the subjects had been taking for at least 8 weeks before the first dose of INCB050465. The maximum dose of ruxolitinib allowed for subjects with baseline platelet count  $\geq 100 \times 10^9/L$  is 25 mg BID, and the maximum dose of ruxolitinib for subjects with baseline platelet count of  $\geq 50 \times 10^9/L$  to  $< 100 \times 10^9/L$  is 10 mg BID.

Subjects receiving dose reductions (but not meeting DLT criteria) during the first 28 days who had not received at least 22 days of the prescribed dose of INCB050465 and ruxolitinib for that cohort were not considered evaluable for the purposes of determining the MTD and were replaced.

The MTD of INCB050465 was planned to be the highest dose level tested that was considered tolerated on the basis of fewer than 2 DLTs in a cohort of 6 subjects. Individual subject dose reductions were made based on events observed at any time during treatment with INCB050465; however, for the purposes of dose cohort escalation/de-escalation, expanding a dose cohort, and determining the MTD of INCB050465, decisions were made based on events that were observed from the first day of study drug administration through and including Day 28. A lower MTD

may have subsequently been determined based on relevant toxicities that became evident after Day 28.

After the 28-day safety evaluation period, safety run-in subjects received additional combination therapy of INCB050465 plus ruxolitinib as long as adequately tolerated with study visits each month and additional laboratory assessments biweekly. INCB050465 administration was QD for total of 8 weeks after the first dose, followed by once-weekly administration at the cohort-specified dose. Measurements and procedures followed those described for the randomized portion. Dose modifications after the 28-day safety evaluation period in the safety run-in cohort followed the dose modification rules in Section [5.5.1](#).

A DLT was defined as the occurrence of any of the toxicities shown in [Table 3](#) occurring up to and including Day 28, except those with a clear alternative explanation (eg, disease progression, other medications) or transient ( $\leq 72$  hours) abnormal laboratory values without associated clinically significant signs or symptoms based on investigator determination. All DLTs were assessed by the investigator using CTCAE v4.03 criteria. Subjects who received at least 22 of 28 doses of INCB050465 and ruxolitinib at the level assigned or had a DLT were considered evaluable for determining tolerability of the dose.

**Table 3: Dose-Limiting Toxicities for Part 1**

Dose-Limiting Toxicities
Nonhematologic Nonhematologic DLT is defined as any clinically significant nonhematologic AE or abnormal laboratory value assessed as unrelated to disease progression, intercurrent illness, or concomitant medication that occurs during the first 28 days of therapy, is assessed as being at least possibly related to study drugs, and meets any of the following criteria: 

• CTCAE Grade 3 AST or ALT for <math>> 7</math> days.

• CTCAE Grade 4 AST or ALT of any duration.

• Grade 3 nausea/vomiting, dehydration, or diarrhea lasting more than 3 days in the setting of optimal supportive medications.

• Grade 3 fatigue lasting more than 5 days in the setting of optimal supportive medications.

• Grade 3 biochemical abnormalities (eg, lipase elevation or bilirubin elevation) will only be considered a DLT if accompanied by clinical consequences. Grade 3 electrolyte abnormalities will only be considered DLTs if related to study drugs and not corrected by optimal replacement therapy or if persisting after 7 days of optimal replacement therapy.

• All Grade 4 nonhematologic toxicities of any duration.

• All other clinically significant nonhematologic AEs that are Grade 3 according to CTCAE v4.03.

Hematologic Myelosuppression and cytopenias are expected outcomes of MF disease processes and MF treatments and per se will not constitute DLTs except as follows: 

• Grade 4 thrombocytopenia with bleeding.

• Grade 4 neutropenia with fever that does not clinically resolve within 7 days in the setting of optimal interventions.

 Anemia will not be considered in the definition of DLT.

Part 1 was conducted at selected clinical study sites (in the United States only). Enrollment was controlled by distribution of enrollment slots to the clinical sites by the sponsor or its designee. The sponsor conducted approximately weekly safety teleconferences with the investigators

[figure not shown]
participating in Part 1 to review subject status and safety findings to ensure safe, appropriate administration. Part 1 has been completed. No DLTs were observed. The treatment groups for Part 2 were determined to be TG10 and TG20.

#### 4.1.2. Part 2: Randomized Portion

Part 2 was to be enrolled and conducted provided that a tolerable dose could be established for INCB050465 in combination with ruxolitinib in Part 1 of the study. Part 2 was planned to enroll approximately 60 subjects randomized 1:1 by block randomization into 2 treatment groups, TG10 and TG20.

[Figure 1](#) shows the study design for Part 2.

**Figure 1: Part 2 Study Design**

[figure not shown]

Enrollment into Part 2 at a given study site is terminated effective with site-specific IRB approval of Protocol Amendment 5.

#### 4.1.3. Part 3 Randomized Portion

In Part 3, all subjects will initially receive INCB050465 at 20 mg QD for 8 weeks in combination with ruxolitinib. After Week 8, subjects will be assigned to 1 of 2 dose groups based on block randomization at the time of entry into the study (using a randomization of 3:2 for TG5 vs TG20 for the first 40 subjects, followed by 1:1 randomization for additional subjects, up to a total of approximately 52 subjects) as shown in [Figure 2](#).

**Figure 2: Part 3 Study Design**

[figure not shown]

As of site-specific approval of Amendment 6, there will be no further enrollment into Part 3 at the given site. Subjects already enrolled into TG5 in Part 3 will continue to receive INCB050465 according to the original randomization for Part 3 and may continue in the study indefinitely unless criteria for discontinuation are met. Subjects already enrolled into TG20 in Part 3 will have the opportunity to cross over to receive 5 mg QD of INCB050465 once they reach Week 8 provided they demonstrate inadequate response to the current dose regimen; an adequate bone marrow reserve; and no evidence of uncontrolled renal, hepatic, cardiovascular, or gastrointestinal disease. A list of requirements for crossover is provided in Section 5.2.3. The TG20 group will be deemed full with enrollment of the 15th subject to that group considering all sites; all further enrollment to Part 3 will be to TG5 at a given site until Amendment 6 has been approved.

#### 4.1.4. Part 4 Randomized Portion

Part 4 of the study is designed to compare different daily dosing regimens and to address the impact of an initial higher dose of INCB050465 on overall response. Subjects will be randomized to one of 2 groups: TG5D will receive 5 mg daily doses of INCB050465 from Day 1 until EOT visit. TG5I/M will receive doses of 20 mg daily for 8 weeks (induction phase), followed by 5 mg daily dosing (maintenance phase). Dosing will continue per the randomized group assignment indefinitely or until discontinuation criteria are met. Note that TG5I/M is identical to TG5 from Part 3; subjects from these 2 groups will be combined in the final analysis. Figure 3 shows the study design for Part 4.

Figure 3: Study Design for Part 4

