## **9.2.      Selection of Sample Size**

The sample size and power calculations for the randomized portion of the study are based on a 2-sample Wilcoxon rank sum test with a normal approximation applied to the test statistic. For a 2-sided Type I error of 0.10 and Type II error of 0.10 with 30 subjects per treatment group, the

test is powered to detect an 11.4 percentage point location shift between the 2 groups in regards to percentage change in spleen volume. The 2 populations are assumed to be normally distributed with a common standard deviation of 14.5.

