#### **9.4.1. Efficacy Analyses**

##### **9.4.1.1. Primary Efficacy Analyses**

The primary endpoint is change in percentage spleen volume from baseline at 12 weeks as measured by MRI (or CT scan in applicable subjects). Statistical comparisons between treatment groups for the primary endpoint will only be performed between subjects randomized to TG5D and TG5I/M + TG5 in Parts 3 and 4 of the study.

A location shift in percentage change in spleen volume between TG5D and TG5I/M accounting for stratification by ECOG performance status at screening (ECOG 0-1 vs 2) will be assessed using a van Elteren test ([van Elteren 1960](#)).

Within each stratum, subjects who discontinue from the study or who have missing values for the Week 12 spleen volume will be imputed as having the largest possible increase in percentage spleen volume and given the lowest rank in the stratum. The subject with the largest percentage reduction in spleen volume in a stratum will be given the highest rank within the stratum. In the case of ties, average ranks will be assigned.

If the randomized portion of the study fails to enroll a sufficient number of subjects in a particular stratum, then the primary endpoint will be assessed using a 2-sample Wilcoxon rank sum test with a normal approximation applied to the test statistic, for purposes of calculation stability. Ranking will be carried out using the same approach but without stratification.

Results for subjects enrolled to TG10 and TG20 will be summarized descriptively with no formal statistical comparisons performed.

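### Part 3 TG5 participants, never randomised against TG5D, are pooled into the primary comparison, with no planned Part 4-only analysis and no single naming of the groups compared

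*Protocol*

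**What the plan says.** **Pooling.** Protocol 4.1.4 describes Part 3 TG5 and Part 4 TG5I/M as the same regimen and states that "subjects from these 2 groups will be combined in the final analysis". The Synopsis (Statistical Methods), Protocol 9.3 and the first paragraph of 9.4.1.1 put the pooled group against TG5D. SAP 5.2 combines participants from all parts, and SAP 7.3.1 compares TG5D with TG5 (TG5I/M).

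**Allocation.** Under Randomization in Protocol 4.1, Part 3 allocated 3:2 between TG5 and TG20; TG5D was not available. In Part 4, "subjects will be randomized on a 3:2 ratio between TG5D and TG5I/M until 25 total subjects have been randomized", and 1:1 after that. Protocol 4.1.3 adds a rule for Part 3 that applies once TG20 has its 15th subject: "all further enrollment to Part 3 will be to TG5 at a given site until Amendment 6 has been approved".

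**Test.** Protocol 9.4.1.1 and SAP 7.3.1 use a van Elteren test stratified by ECOG 0-1 vs 2. SAP 7.1 limits strata to those used in randomisation. SAP 7.3.2 lists subgroups by disease subtype and baseline spleen volume only.

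**Naming.** The second paragraph of Protocol 9.4.1.1 describes the test differently from the first: "A location shift in percentage change in spleen volume between TG5D and TG5I/M accounting for stratification by ECOG performance status". SAP 7.2.1 states the primary hypothesis for TG5D and TG5I/M without TG5, as does the opening paragraph of SAP 7.3.1.

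**The concern.** Randomisation protects the comparison of TG5D with TG5I/M inside Part 4. It does not protect the comparison of TG5D with Part 3 TG5, because no Part 3 participant could have been allocated to TG5D. All the Part 3 participants sit on one side of the test. If they differ from Part 4 participants in case mix, sites or care, that difference is read partly as a treatment effect. Protocol 9.3 and SAP 3.6 state the 10% error risk without qualification, and Protocol 4.2 relies on block randomisation as the safeguard against bias. Neither statement covers this part of the comparison, and no planned analysis would show whether the result depends on it.

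The naming conflict is a separate matter. Read literally, the plan leaves open whether Part 3 participants belong in the primary p-value. SAP 10.1 records no changes to protocol-defined analyses, so it does not settle the question.

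**Working it through.** **1. Inputs.** Protocol 9.2: "For a 2-sided Type I error of 0.10 and Type II error of 0.10 with 30 subjects per treatment group"; "test is powered to detect an 11.4 percentage point location shift between the 2 groups"; populations "assumed to be normally distributed with a common standard deviation of 14.5". Protocol 4.3.1: about 5 subjects in Part 3, about 55 in Part 4. Protocol 4.1: 3:2 for the first 25 in Part 4, then 1:1.

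**2. The plan's own power.** Simulating the Wilcoxon rank sum test at 30 vs 30, shift 11.4, SD 14.5, two-sided alpha 0.10 gives power 0.90 and type I error 0.10. The formula with the Wilcoxon efficiency 3/π gives Φ(11.4 / [14.5 × √(2/(30 × 3/π))] − 1.645) = Φ(2.976 − 1.645) = 0.908. The stated 90% is reproduced.

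**3. How many Part 3 participants are pooled.** The first 25 in Part 4 split 15 TG5D and 10 TG5I/M. Another 15 in each group gives 30 TG5D and 25 TG5I/M, or 55 in all, as planned. The figure of about 5 for Part 3 covers both of its groups, so at 3:2 about 5 × 3/5 = 3 are TG5, and the pooled group is 25 + 3 = 28. If all 5 were TG5, it would be 25 + 5 = 30.

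**4. Bias.** Assumption, not in the documents: Part 3 participants differ from Part 4 participants by s percentage points for reasons other than treatment. With k of n pooled participants from Part 3, bias = (k/n) × s.

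| Part 3 share | s | Bias (points) | Simulated type I error |
|---|---|---|---|
| 3 of 28 | 5 | 3/28 × 5 = 0.5 | about 10.2% |
| 3 of 28 | 10 | 3/28 × 10 = 1.1 | about 10.9% |
| 5 of 30 | 5 | 5/30 × 5 = 0.8 | about 10.6% |
| 5 of 30 | 10 | 5/30 × 10 = 1.7 | about 12.1% |

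Repeated simulations differ by a few tenths of a point. A normal approximation for 5 of 30, Φ(−1.645 + b/SE) + Φ(−1.645 − b/SE) with SE = 14.5 × √(2/30) = 3.74, runs slightly higher: 10.8% at b = 0.83 and 13.3% at b = 1.67.

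**5. A smaller Part 4.** SAP 5.2 and 10.2.3 say that the study, or its enrolment, ended early, without counts. As an illustration only, suppose Part 4 stopped at its first 25 (15 vs 10) with 5 TG5 from Part 3. The share is then 5/15, and a 10-point difference gives a bias of 5/15 × 10 = 3.3 points and a type I error of about 15%.

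**6. Part 4-only test.** At 30 vs 25, simulated power for 11.4 points is 0.873. The formula gives Φ(11.4 / [14.5 × √((1/30 + 1/25) × π/3)] − 1.645) = 0.883.

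**7. A stratum for part.** A Part 3 stratum holds no TG5D participant, so it has no between-group contrast and adds nothing to the van Elteren statistic. Stratifying by part gives the Part 4-only test under another name.

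**8. The TG20 cap.** Counting Part 3 alone, 15 TG20 subjects at 3:2 need 15 / (2/5) = 37.5, so about 38 subjects. Adding Part 2 (20 subjects at 1:1, about 10 in TG20), the cap is met only if all of about 5 Part 3 subjects go to TG20. If Part 1's 20 mg cohort also counts (6 assumed), the total is already about 16. The documents do not say which count applies.

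**The case against.** The pooling is open and pre-specified: Amendment 6 brought in Part 4 and the pooling together, and the planned sizes fit it. Regimen, eligibility criteria and central imaging reading are the same in both parts. Amendments 5 and 6 are about 7 months apart, and because Part 3 closes site by site, its enrolment can overlap with Part 4 elsewhere. A 10-point difference between parts would be nearly the whole 11.4-point design effect. SAP 5.2 treats TG5 and TG5I/M as one group, so the naming conflict may be only editorial. All of this stands, and it is why the size here is modest and why replacing the pooled primary analysis is not clearly better. It does not supply a randomised comparison for the Part 3 participants, or a planned check on their influence.

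A reader might infer from "all further enrollment to Part 3 will be to TG5 at a given site until Amendment 6 has been approved" that some TG5 participants were in fact assigned without randomisation. The documents do not support that. The rule is conditional on the TG20 cap, no section says that the cap was reached, and Protocol 4.1 describes Part 3 subjects as randomised 3:2. Such assignment could happen; it is not reported to have happened.

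The Part 4-only test is not free of time effects either. The ratio changes after 25 subjects, so 15/30 of TG5D but 10/25 of TG5I/M enter early; a 10-point drift within Part 4 would give (0.50 − 0.40) × 10 = 1.0 point of bias. Adding period strata lowers power to about 0.869 and, with ECOG, makes four cells in a plan that already expects sparse ECOG strata.

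**Conclusion.** The point holds as a missing supporting analysis and an unresolved definition. For the Part 3 participants the stated 10% error rate does not rest on randomisation. At planned numbers, with an assumed 5- to 10-point difference between parts, the type I error stays between about 10.2% and 12.1%. That does not show the pooled analysis to be invalid. The figures depend on the assumed difference and on planned rather than actual counts, and the exposure grows if Part 4 closed small. The naming conflict needs correcting whatever the bias.

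**What to change.** In SAP 7.3.1, pre-specify the ECOG-stratified van Elteren test in Part 4 participants only, TG5D vs TG5I/M, reported beside the pooled analysis. State that a conclusion of a difference should be consistent across both. Report the number of Part 3 TG5 participants in the pooled group and whether any were assigned after TG20 was deemed full. Name the same primary comparison in Protocol 9.4.1.1 and SAP 7.2.1 and 7.3.1.

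The cost is one extra analysis and a few wording changes. At planned sizes the Part 4-only test has about 87% power rather than 90%, so a somewhat weaker p-value there should be read with its smaller sample in mind.

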#### 4.2. Measures Taken to Avoid Bias

This is an open-label comparison of 2 dose regimens of INCB050465. Subjects will be randomized by block randomization. Measurements of safety and efficacy are objective measurements.

## **4.3. Number of Subjects**

### **4.3.1. Planned Number of Subjects**

Part 1 was expected to enroll 9 to 18 subjects (10 were enrolled), Part 2 was planned to enroll a total of 60 subjects before termination; because Part 3 was added, only 20 subjects were enrolled. Part 3 was expected to enroll approximately 52 subjects; approximately 5 subjects may be enrolled. Part 4 will enroll approximately 55 subjects. Twenty or more clinical sites will participate.

### **4.3.2. Replacement of Subjects**

As noted in Section 4.1, a minimum of 3 subjects must be deemed evaluable for each cohort of Part 1 that is enrolled. If a subject becomes nonevaluable either because of dose compliance < 80% (correct administration of INCB050465 for 22 of 28 days in the safety evaluation period) or withdraws because of an AE that does not meet the criteria for a DLT, then an additional subject will be enrolled to ensure the minimum evaluable cohort is achieved.

